### **Study design related to specific *Aim 1*: Anorectal pathophysiology of LARS patients**

Studies are planned to include a heterogeneous group of LARS patients with a broad scale of symptoms. We will study 30 patients recruited from a pool of postoperative patients who are under the care of our Department. The department has a large cohort of patients with LARS and it is anticipated that it will be easy to recruit the patients.

#### **Inclusion Criteria:**

1. Patients 18 years of age or older with history of LARS over 3 months.

2. Informed, written consent by the patient

**Exclusion Criteria:**

1. Patients who are not willing to undergo the specified tests in this study
2. Pregnant women

The studies on LARS patients will focus on pathophysiological studies where we describe the expulsion characteristics, with focus on anal canal opening related to rectal mechanosensory data and to changes in the anorectal angle during defaecation. We will study expulsions at the urge-to-defecate level for the patients and we will correlate to data obtained by conventional technologies and to patient characteristics such as age, and symptoms as well as to risk factors. The study subjects will also be tested with conventional expulsion testing, defecography, rectal bag distension, and ARM. The studies will determine endpoints of clinical value such as expulsion time and velocity, maximum angle difference, pressure signatures and geometry changes.

**Expected Results and Milestones:** The expected outcome is that the device will perform as shown in the previous human experiments (n>60) where no adverse effects have been recorded. We anticipate successful access in LARS patients with no device-related adverse events or device malfunctions. Completion of the study is expected to derive outcome measures reflecting the defecatory function as the major impact.

**Potential Pitfalls and Alternative Strategies:** According to the ISO 13485 standard, the device is an insertable low risk device since it will reside inside the body for less than one hour and there is no radiation exposure. All materials are medical grade and the design and mechanical properties chosen after input from KOLs in USA and Europe. Assessment for safety in the above reported preliminary studies and in testing during the developments will not fully recapitulate all the conditions in LARS patients. We will ask the investigators to be alert and retract the device instantly if it suddenly stops working as “alarmed” by the device, which could be indicative of a short circuit. We will work with safety experts to fully mitigate any issues as we have done with other projects. Another concern relates to retraction of the device if it cannot be defecated. To avoid the need for endoscopy, the device will have a thin string attached in the anal end. The string will be the same thin soft type as used in tampons to avoid interference with the mechanosensory properties of the anorectum. If enrollment is slower than expected, we will make an extra effort to recruit patients, but this is hardly to be anticipated considering the high incidence of LARS in our cohort of patients.

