### **Reference testing techniques**

**Anorectal Manometry (ARM) with balloon expulsion testing (BET)** will be conducted with a standard single-use 8ch anorectal catheter (G-90150, MMS, Enschede, Netherlands). The catheter will be inserted with the subjects lying inside position with bent hip and knees. The bag will be placed in the rectum and pressure will be measured at 0.5cm distance in the anal canal. The following parameters will be evaluated: resting anal pressure, maximum anal squeeze pressure, the recto-anal inhibitory reflex (RAIR), urge volume, maximum tolerable volume, and expulsion time for the 50ml balloon.

**Defecography (fluoroscopy or MRI)** will be used as a reference for Fecobionics. A water-soluble paste will be injected into the rectum and serial x-rays will be taken during defecation. Defecography will be used to study several anorectal characteristics. The height of the colorectal anastomosis, any abnormality at the anastomosis such as narrowing, orientation of neo-rectum will be assessed in addition to usual measurements of the anorectal angle and the position of the pelvic floor at rest or during Valsalva (perineal descent). The presence of rectocele, rectal intussusception, and the ability to expel rectal contents will be evaluated. Balloon proctography can simplify the procedure of examining the ability to evacuate by providing a quick and clean test with minimal radiation.

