### Specific Aim 1: Anorectal pathophysiology of LARS patients

Objective: use fecobionics to obtain physiological and pathophysiological signatures of anorectal function in a heterogeneous group of LARS patients. Based on the epidemiology and symptomatology of LARS, it is expected that the heterogeneous group will contain an almost equal number of LARS patients with incontinence, frequency and urgency, and those primarily with constipation and feelings of incomplete emptying. Due to the spread (heterogeneity) in the patient group regarding symptoms, regression analysis will be the primary statistical tool to associate symptoms with experimental findings. We will also compare to age- and sex-matched healthy controls from already conducted studies.

Milestone: Describe the mechanosensory signature, variation of the measured variables, and computed endpoints in LARS patients.

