backward) during the expulsion indicate the usefulness of this kind of measurements. For example, the entrance of the device into the canal as well as the anal relaxation can be assessed. The right panel shows the front pressure as function of the rear pressure. This is a novel representation corresponding to the well-known preload-afterload analysis of cardiac function. Human data from our preliminary data are shown in figure 3.

**Figure 3** shows data from a healthy subject (AB), a patient with fecal incontinence (CD) and chronic constipation (EF). The left panels are the pressure-time plots useful subdividing defecations into phases. The right panel is the front-pressure as function of the rear pressure. Both types of analysis show marked differences between the subjects. In general, the healthy subjects use a few pressure increases (abdominal contractions) to expel the device. The FI subject is characterized by a low anal sphincter pressure and the device pops out by itself. The constipation patient cannot expel the device despite many attempts. Other data (not shown) based on gyroscope data also demonstrate distinct differences between subjects.

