### **Clinical Work Flow for the integrated device.**

This section pertains to the procedures related to use of Fecobionics. All tests prior to Fecobionics are done per department standards. The patient is instructed about the tests. The integrated device is calibrated in a one-step procedure. Similar to the conventional expulsion test, the device is placed in the rectum by manual insertion with the person lying on the side. The bag is distended with simultaneous recording of symptom level until urge to defecate. Volume is recorded. When the urge level is reached, the patient will move to the toilet chair for attempting to expel it. The patient will report sensory data. Most patients who do not suffer from constipation will be able to expel it within 1-2 minutes. If the patient fails to expel the device by himself, the physician or nurse can, if deemed necessary, pull it out by traction of a tiny thread attached to the front end (like the thread used for tampons). The thread is 50 cm long so even if the device relocates to the left side of the colon, it can still gently be pulled out. In the worst case, an endoscope can be used to pull it out.

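### No analysis is specified for patients who cannot expel the device or balloon, so ordinary use of the named methods could weaken the symptom association

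*Combined protocol and SAP*

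**What the plan says.** **Endpoints.** The study design for Aim 1 names "endpoints of clinical value such as expulsion time and velocity, maximum angle difference, pressure signatures and geometry changes". Reference testing techniques adds, for the conventional tests, "urge volume, maximum tolerable volume, and expulsion time for the 50ml balloon".

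**Main analysis.** Specific Aim 1 states that "regression analysis will be the primary statistical tool to associate symptoms with experimental findings". It expects an "almost equal number of LARS patients with incontinence, frequency and urgency, and those primarily with constipation and feelings of incomplete emptying".

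**Failure to expel is foreseen.**
- Approach, describing Figure 3: "The constipation patient cannot expel the device despite many attempts".
- Clinical Work Flow: "If the patient fails to expel the device by himself, the physician or nurse can, if deemed necessary, pull it out". The same section expects expulsion in 1–2 minutes for most patients without constipation.
- Potential Pitfalls: "Another concern relates to retraction of the device if it cannot be defecated". It also tells investigators to "retract the device instantly if it suddenly stops working", which is a separate reason for an attempt to end.

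**Named methods.** The data analysis section gives mean±SD if normal, ANOVA where appropriate, single and multiple regression, and SD/mean. For sample size it adds limits of agreement, using preliminary balloon and Fecobionics expulsion times. It has no censoring rule, failure category or missing-data rule for a failed attempt. The safety section will collect procedural duration and an adverse event form, but neither separates expulsion from removal.

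**The concern.** A patient from whom the device is removed has an expulsion time known only to exceed the removal time, and has no expulsion velocity. The same holds for time on the balloon test.

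Other endpoints are touched less directly. The Impact section ties geometry to entry into the anal canal. Approach divides defecation into phases that include entry. The data analysis section uses the rear–front pressure difference to fix those phases. The Aim 1 design studies the angle during defecation. Signals exist during a failed attempt, but the parts that need entry or passage may be missing or not comparable with a completed expulsion.

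Non-expellers are unlikely to be a random subset, because the plan itself links slow or failed expulsion to constipation, one of the two symptom types under study. With silence in the plan, the two easy choices are to drop these patients or to enter the removal time as if it were an expulsion time. Either could shrink the association that the primary analysis is meant to estimate. Because removal is left to staff judgement, its timing could also depend on symptoms, and either choice could then create an association where none exists.

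**Working it through.** **1. What can be reproduced.** The plan gives no failure rate, removal-time distribution or expulsion-time mean or SD, so it has no figure of its own to reproduce on this point. The sample size of 30 cannot be rebuilt either, since δ and σ are not stated. With the plan's formula, (1.96 + 0.84)/√30 = 0.511 is the δ/σ that it implies.

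**2. How many patients.** Half of 30 is about 15 constipation-type patients. If 10–50% of these fail (assumed), 1.5 to 7.5 of the 30 are affected, or 5–25% of the cohort. The illustration below uses 10–40% of the whole cohort. If all failures came from the constipation-type half, 40% would mean 12 of 15, so the upper end is severe.

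**3. Assumed model.** n = 30; symptom score x ~ N(0,1); log time T = 0.5x + error of variance 0.75, so the true slope and correlation are 0.5. Log removal time is C. The attempt fails if T > C, with probability q, and the recorded value is min(T, C). There were 4,000 simulated trials per scenario, two-sided 5%. Power with all times observed is about 83%.

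**4. Closed-form check of the slopes.**
- Removal time entered: expected slope = ρ(1−q) + γq, where γ is the slope of C on x. With γ = 0 the share kept is 1−q: 90/80/70/60%.
- Expellers only, common removal time c: with λ = φ(c)/(1−q) and V = 1 − cλ − λ², the share kept is V/[1 − 0.25(1−V)]. At q = 0.10: c = 1.282, λ = 0.195, V = 0.712, share 0.712/0.928 = 77%. At q = 0.40: c = 0.253, λ = 0.644, V = 0.422, share 0.422/0.856 = 49%.

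Both agree with the simulation.

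**5. Simulation, failures 10/20/30/40%.**

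| Removal time | Analysis | % of true slope | Power, % |
|---|---|---|---|
| Common | Expellers only | 76/65/56/49 | 64/52/40/30 |
| Common | Removal time entered | 90/80/70/60 | 81/80/78/73 |
| Common | Cox | – | 77/76/76/74 |
| Common | Censored lognormal | 101–102 | 84/83/83/79 |
| Varies, unrelated to symptoms | Expellers only | 89/83/79/78 | 72/63/54/47 |
| Varies, unrelated to symptoms | Removal time entered | 90/80/69/60 | 79/73/63/50 |
| Varies, unrelated to symptoms | Cox | – | 76/76/70/69 |
| Varies, unrelated to symptoms | Censored lognormal | 100–101 | 84/82/78/76 |

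**6. Earlier removal in more symptomatic patients, no true association.** Set ρ = 0 and γ = −0.5 (assumed). The formula in step 4 gives false slopes of −0.05/−0.10/−0.15/−0.20 when removal time is entered. False-positive rates at nominal 5%: removal time entered 5/9/16/26%; expellers only 6.5/7.8/10.2/11.3%; Cox 5–6%; censored lognormal 6–6.5%.

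**7. Different assumptions.** A second simulation used median time 90 s, slope 0.50, residual SD 0.8 and a common removal time giving 10/23/38% failures. Dropping gave slopes 0.39/0.32/0.26 with power 72/55/37%. Entering removal time gave 0.45/0.39/0.31 with power 87/86/80%, against 87–89% with complete data. The pattern is the same.

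**8. Precision of the proportion expelled (Clopper-Pearson 95%).** 27/30: 73.5–97.9%. 18/30: 40.6–77.3%.

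**The case against.** The best counter-case has several parts.

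- **Silence is not a wrong method.** A reader might infer that the plan will drop non-expellers or enter their removal times. It says neither, and regression does not exclude a censored model. This stands: the harm is conditional.
- **No failure rate in LARS is shown.** A reader might infer that failures will be common in this cohort. The one non-expeller described has chronic constipation, not LARS. This stands, and every magnitude above is assumed.
- **Entering the removal time costs little power when that time is common to all.** Power is 81/80/78/73%, about the same as Cox at 77/76/76/74%. This stands; there the cost is mainly slope bias, and the power case is against dropping patients.
- **The false-positive result depends on an assumed link.** No passage supports the figure of −0.5, and at 10% failures the methods hardly differ. This stands; it shows a possibility only.
- **The model flatters the remedy.** The data came from the lognormal model being fitted, and patients who would never expel were not simulated. The single symptom score is also a convenience, because Aim 1 describes two symptom types. This stands.
- **The balloon test may have a local time limit**, since tests before Fecobionics follow department standards. Even so, an analysis rule would be absent.
- **The study is exploratory and has no single primary endpoint.** This lowers the severity, but regression on symptoms is still named as the primary tool.

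A narrower reading is also tempting: that only time and velocity are affected. The plan's own descriptions of phases and anal entry do not support that limit.

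**Conclusion.** The point holds in conditional form. The plan anticipates non-expulsion, ties it to symptoms, and names only methods that ordinarily need an observed value. Time is right-censored and velocity undefined for these patients; other passage-dependent measures may be incomplete or not comparable.

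Under the assumed model with a common removal time, both shortcuts shrink the slope, and dropping patients is clearly the worse one. A right-censored model removes the bias if removal is unrelated to the unseen time given symptoms.

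The documents support no direction of bias for balloon–Fecobionics agreement. The statement that the device stays in the body under one hour concerns device risk and is not an analysis cut-off. The plan should be amended, but the gap does not invalidate the study.

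**What to change.** For Fecobionics and the balloon test:

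- Record expelled yes/no, attempt duration at expulsion or removal, and reason for ending (failed expulsion or malfunction). Do not count malfunction removals as failed expulsions.
- Report the proportion expelled with an exact confidence interval.
- Analyse expulsion time against symptoms with one pre-specified right-censored regression, such as Cox or censored lognormal. Censor non-expellers at their recorded removal time, and state the assumption that, given symptoms, removal is unrelated to the unseen time.
- Report velocity and other passage-dependent measures by whether expulsion occurred, labelled so.
- Compare the two tests by a paired expelled/not-expelled table. Restrict limits of agreement for time to patients who expelled both, labelled so.

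The cost is a short analysis paragraph and three data fields, which may not be recoverable if not recorded at the test. The effect becomes a time ratio or hazard ratio rather than a mean in seconds. Type I error may be slightly raised at n = 30 (about 6%), and Cox gives up some power against fully observed times. The timing of device removal stays with the investigators.

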**Data analysis including statistics and sample size determination.**

A number of biomechanical parameters will be computed from the recorded data. These parameters include but are not limited to:

- Pressure difference between the rear and front ends (a measure of anal sphincter relaxation and key to the determination of phases of the defecatory process)
- Orientation and bending of Fecobionics for assessment of the anorectal angle

- Velocity of expulsion (as measured from the time difference between sensor data)
- Tension
- Strain (deformation) and displacement

Definitions of tension, strain and displacements can be found in the two books by the [name]. Sensory measures and clinical data will be related statistically to the mechanical measures. Endpoint data will be expressed as mean±SD if they can be considered normally distributed. Significance of the differences between two methods will be evaluated by ANOVA where appropriate and by multiple and single regression analysis. The results will be considered statistically significant when p<0.05 (2-tailed). Multiple regressions will be used to evaluate risk factors using causal and predictive analysis. Repeatability and distribution will be determined based on coefficient of variation (SD/mean) and used to evaluate accuracy.

The projected number of subjects, n, required to test a null hypothesis is given by the following equation:

$$n > \left[ \frac{[Z_{2\alpha} + Z_{2\beta}] \sigma}{\delta} \right]^2$$

where  $\alpha$  is the required probability of a Type I error,  $\beta$  is the required probability

of a Type II error,  $\delta$ , is the estimated difference between the means of two comparison groups, and  $\sigma$  is the estimated standard deviation of the means in each of the two comparison groups. We assume  $2\alpha < 0.05$  ( $Z_{2\alpha} = 1.96$ ) and  $2\beta < 0.10$  ( $Z_{2\beta} = 0.84$ ). We assume the values of mean difference, d, and standard deviation, s, from previous experience in the clinical laboratory and from reported data in the literature on the involved patient groups and the sensitivity and specificity of current tests. An alternative method is to use sample size estimation based on the Altman-Bland analysis (<http://wwwusers.york.ac.uk/~mb55/meas/sizemeth.htm>). Preliminary data on expulsion time using BET and Fecobionics were used in the sample size analysis. Data variation (SD, SE) was computed for preliminary data. The confidence interval for the 95% limits of agreement was computed and n was determined. For both analyses, given the exploratory nature of the study, we consider a heterogeneous group of patients and that 80% of operated patients will develop LARS. Using these boundaries and criteria, we arrived at a sample size of 30 in the Aim 1 study for evaluation of statistical significance, association and risks. Though the material may be too small to account for confounders, we will obtain clear indications of risks and causes. For the comparison with previously studied subjects, we have a pool of 35 healthy asymptomatic subjects, 20 patients with FI and 15 patients with constipation to compare with.

**Clinical Assessments of device safety:** Fecobionics have now been used in more than 70 human studies without any incidents or adverse effects. In addition, a safety study has been performed in 12 pigs without any device related issues or damage to anorectal mucosa (yet unpublished data). Since Fecobionics is still an experimental device, we will pay attention to safety. If any safety issue occurs, it will be characterized and reported. Additional data obtained will include procedural duration, sensation

including pain, inspection of the anus after the expulsion in addition to any adverse events that may occur. Follow-up physician interviews will obtain qualitative measures of device performance and utility. Unanticipated adverse device effects (**UADE**) are defined as any serious adverse effect on health or safety or any life-threatening problem or death caused by, or associated with a device if that effect, problem, or death was not previously identified in nature, severity, or degree of incidence in the investigational plan or application, or any other unanticipated serious problem associated with a device that relates to the rights, safety, or welfare of subjects. The procedure for reporting any adverse event (whether device-related or not) is to fill in all sections of an adverse event case report form. Details and symptoms associated with the event will be reported in the narrative section on the Narrative/Notes CRF. It will be the responsibility of the clinical study investigator to inform the IRB of adverse events (whether device related or not) according to their requirements.

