## **Technological background**

In the proposed studies it is important to compare the new technology, Fecobionics, to current state-of-the-art reference technologies. We expect Fecobionics to provide data that cannot be obtained with current technology and to reduce variation in measured variables.

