### **New technology**

**Fecobionics** is a novel device, a simulated faeces, that we currently are testing in healthy subjects and in patients suffering from fecal incontinence and constipation (RGC funded proposal “Unraveling anorectal function and biomarker signatures in patients suffering from subtypes of defecatory disorders”). Fecobionics records pressures, orientation, bending, shape, and viscoelastic properties during defecation. It is made of a 10 cm long and 12 mm wide core of medical grade resin that contains multiple electronic sensors and circuit boards. A bag is mounted on the bendable core. Pressure transducers are placed at the front, rear and inside the bag, in addition to two gyroscopes for orientation and angle measurements. A novelty of Fecobionics is that it measures pressures in axial direction (in the direction of flow) in contrast to current technologies and that it integrates almost all current anorectal functional tests into a single test that only takes minutes to perform without the use of radiation or expensive equipment. Since the Fecobionics technology was developed by the PI [name], we are currently the only clinical research group with access to the technology. This gives us a unique opportunity to become the leaders in the field.

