### Data collection:

Patients will be assessed at baseline and following will be recorded for all patients:

- Demographic data
- Body Mass Index (BMI)
- Significant Past Medical and Surgical History
- Obstetric History (female patients only)
- Rectal Cancer stage: TNM staging, location of tumour from anal verge on preop image

- Rectal Cancer treatment
  - o Neoadjuvant chemoradiotherapy/radiotherapy/chemotherapy
  - o Surgery – Open/Laparoscopic/Robotic/TaTME, level of anastomosis
  - o Post-operative complications
  - o Postop chemotherapy / radiotherapy
  - o Timing of defunctioning stoma (ileostomy / colostomy) closure
- LARS questionnaires: to assess Quality of life associated with LARS (Figure 4)

All patients will undergo the following tests:

- Integrated Fecobionics anorectal test (see clinical workflow below)
- High Resolution Anorectal Manometry (ARM) to assess resting and squeeze pressures, sensitivity, rectal capacity and recto-anal inhibitory reflex.
- Conventional balloon expulsion test
- Defaecography

Clinical data will be recorded and stored electronically in the hospital server. Completed questionnaires will be recorded and entered into database software and stored in the hospital server.

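### Every patient has all the tests, but the plan names no paired analysis and no agreement analysis for comparing the methods

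*Combined protocol and SAP*

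**What the plan says.** **Design.** Under Data collection, the list of tests opens with "All patients will undergo the following tests". It names Fecobionics, high-resolution manometry, the conventional balloon expulsion test and defaecography.

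**Purpose.** Technological background states: "In the proposed studies it is important to compare the new technology, Fecobionics, to current state-of-the-art reference technologies". The comparison is therefore an intended use of the data.

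**Analysis.** The section on data analysis and sample size gives method comparison one sentence: "Significance of the differences between two methods will be evaluated by ANOVA where appropriate and by multiple and single regression analysis". It does not say whether the ANOVA is one-way or repeated-measures, or what kind of regression is meant. Repeatability is to be described by a coefficient of variation.

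**Sample size.** The same section gives a formula in which delta "is the estimated difference between the means of two comparison groups". Its sigma is likewise defined per group and not as the SD of within-patient differences. Neither has a value. It then names the Bland-Altman approach as an alternative and says that limits of agreement were computed, with preliminary balloon and Fecobionics expulsion times as the data. The result is 30 patients.

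**Other uses of the same tools.** Specific Aim 1 makes regression the main tool for relating symptoms to findings. The text after the exclusion criteria plans correlation with the conventional tests. The sample-size section also lists separate, previously studied pools: 35 healthy subjects, 20 patients with faecal incontinence and 15 with constipation.

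**The concern.** Two readings from one patient usually share that patient's own level. An analysis that ignores this leaves between-patient variation in the error term. With a positive correlation, its standard error for the difference between methods is too large, and a real offset may fail to reach significance. In a study meant to show how a new device relates to its references, such a result could be reported as no difference.

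Regression does not fill the gap. A non-zero slope says that the two methods move together. They can do so closely while one reads consistently higher.

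An offset is plausible here. The reference expulsion test uses a fixed 50 ml balloon, whereas the Fecobionics bag is filled to the urge level, so the two expulsion times are taken under different conditions. Limits of agreement would show such an offset and its spread. The team used them for sizing, but the analysis text leaves them out.

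**Working it through.** **1. The plan's own figure.** The stated n = 30 cannot be reproduced, because delta and sigma have no values; the text says only "We assume the values of mean difference, d, and standard deviation, s, from previous experience in the clinical laboratory and from reported data". Solving the plan's formula backwards with its two Z values:

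- delta/sigma = (1.96 + 0.84)/sqrt(30) = 2.80/5.477 = 0.511
- check at 0.5: (2.80/0.5)² = 31.4, so 32 patients

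By the Bland-Altman route, n = 30 gives a 95% interval of ±1.96 × sqrt(3/30) × s = ±0.62 s around each limit, where s is the SD of the differences. No target width is stated.

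**2. Inputs for the check.**

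| Input | Value | Source |
|---|---|---|
| Patients, each with both methods | 30 | documents |
| Two-sided significance level | 0.05 | documents |
| Bias between methods | 0.5 SD | assumed; close to the 0.511 implied above |
| Correlation between methods, rho | 0, 0.3, 0.5, 0.7 | assumed; not in the documents |
| SD of each method | equal, set to 1; normal data | assumed |

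**3. Standard errors of the mean difference.**

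- Unpaired: sqrt(2/30) = 0.258
- Paired: sqrt(2(1 − rho)/30)
- Ratio, unpaired to paired: 1/sqrt(1 − rho)

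At rho = 0.5 the paired value is sqrt(1/30) = 0.183, and 0.258/0.183 = 1.41.

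**4. Power and true error rate.** Paired power comes from the non-central t distribution with 29 degrees of freedom and non-centrality 0.5 × sqrt(30)/sqrt(2(1 − rho)). At rho = 0.5 this is 2.739/1 = 2.74. Simulation agrees with these values and supplies the unpaired columns.

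| rho | Ratio of standard errors | Power, unpaired | Power, paired | True type I error, unpaired |
|---|---|---|---|---|
| 0 | 1.00 | 48% | 47% | 5% |
| 0.3 | 1.20 | 47% | 61% | 2% |
| 0.5 | 1.41 | 47% | 75% | 0.7% |
| 0.7 | 1.83 | 46–47% | 93% | below 0.1% |

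With positive correlation the unpaired test is conservative. It loses power and creates no false positives.

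**5. Regression.** Suppose two methods agree except for independent error of equal size. The least-squares slope of one on the other then averages the reliability of the predictor: 0.95, 0.90, 0.80 and 0.70 at assumed reliabilities of 0.95, 0.9, 0.8 and 0.7. A slope below 1 is therefore no evidence of disagreement. The test of zero slope stays valid under its null hypothesis, but it is a test of association.

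**The case against.** **The plan does not state a wrong test.** A reader might infer that it prescribes a one-way ANOVA. It does not: the sentence limits ANOVA to where it is appropriate, and repeated-measures ANOVA with two methods is the same as a paired t-test. This stands. The loss shown above is conditional on the unpaired reading.

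**The wording about two groups is weak evidence.** It defines symbols in the sample-size formula. That formula has no factor of 2, so it has the one-sample or paired form, and comparisons with separate pools are also planned. This stands, and the point does not rest on that wording.

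**No slope is to be tested against 1.** A reader might infer that the planned slope is wrong, or that it will signal disagreement where there is none. No section plans such a test or reads a slope as calibration, and nothing says the regression must be ordinary least squares. The attenuation is only a warning against a later misreading.

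**No comparison of mean pressures is planned.** Under New technology the device is distinguished because "it measures pressures in axial direction (in the direction of flow) in contrast to current technologies". A reader might infer that a test of equal means between manometry and Fecobionics pressures is intended. No section proposes one, and correlation is what the text describes.

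**The study is exploratory, and its main tool is symptom regression.** This is true and limits the weight of the point. It does not remove it, because the plan calls the comparison with reference technologies important.

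**The team knows about agreement analysis.** It does, since it was used for sizing. That makes its absence from the analysis text a mismatch between sizing and analysis that is easy to repair.

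**Conclusion.** The concern holds in a limited form. The data for method comparison are paired. The analysis text names neither a paired nor an agreement analysis, and it assigns regression to a question about differences that regression of one method on another does not answer. The limits of agreement used in sizing are not carried into the analysis.

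If the ANOVA is run unpaired, power at a 0.5 SD bias stays near 47%, against 61% to 93% paired for rho from 0.3 to 0.7. At rho = 0 nothing is lost. These figures assume the correlation, the bias, equal SDs and normal data, none of which the documents supply. If the ANOVA is run as repeated measures, the power loss disappears and what remains is the missing agreement analysis.

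The documents do not support saying that the standard errors or the slope are wrong as planned. The change is worth making because it settles the reading at no cost in data.

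**What to change.** Replace the method-comparison sentence in the data analysis section with text that does the following.

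- **Quantities both methods measure in the same units** (expulsion time, anorectal angle, urge volume): report the within-patient mean difference with its 95% confidence interval, from a paired or repeated-measures analysis.
- **Expulsion time:** the clinical work flow foresees patients who cannot expel the device, and they have no observed time. State a rank-based or censored-data method for paired times, so that these patients are not dropped.
- **Agreement:** report Bland-Altman limits of agreement with confidence intervals, to match the sample-size section. For expulsion time, say how failures to expel are handled.
- **Regression and correlation:** keep them for association, including symptoms against findings and device against conventional tests. State that a least-squares slope will not be read as agreement.
- **If a slope is wanted:** use an errors-in-variables method such as Deming regression. The work flow describes one expulsion with no stated replicate, so the ratio of error variances would have to be assumed, and the result shown over a range of ratios.
- **Separate pools** (35 healthy, 20 incontinence, 15 constipation): keep unpaired ANOVA.

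The cost is a revision of the analysis text before the data are analysed. No extra patients or measurements are needed.
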